## **10.0 DATA AND PROTOCOL MANAGEMENT**

10.1 Data Entry: All data will be entered to the Department of Genitourinary Medical Oncology Oracle database (GURU). GURU is a password protected database with an audit trail. Data can be collated with a unique GURU identification in order to de-link information. The minimum required fields will be entered to the MDACC required data collection systems (CORe/PDMS). Data will be derived from the patient chart and the Principal Investigator will be the final arbiter of any conflicting entries. The Principal Investigator will be the final arbiter of response, toxicity, or progression should a difference of opinion exist.

Patient Confidentiality: In order to maintain patient privacy, all database generated case report forms, study drug accountability records, study reports and communications will identify the patient by initials and the assigned patient number. The patient's confidentiality will be maintained and will not be made publicly available to the extent permitted by the applicable laws and regulations (21CFR312.63, 21CFR312.68).

10.2 Study Drug Management

Returned or expired study drug will be destroyed on site per MDACC Investigational Pharmacy policies.

## **11.0 MEASUREMENT OF EFFECT**

For the purposes of this study, patients should be reevaluated for response every 12 weeks. In addition to a baseline scan, confirmatory scans should also be obtained no sooner than 6 weeks following trial completion to document cases of objective response.

11.1 Definitions

Response and progression will be evaluated in this study using the new international criteria proposed by the Response Evaluation Criteria in Solid Tumors (RECIST) Committee, with rationale for modification as noted below in Section 11.1.5. Changes in only the largest diameter (unidimensional measurement) of the tumor lesions are used in the RECIST criteria. Note: Lesions are either measurable or non-measurable using the criteria provided below. The term "evaluable" in reference to measurability will not be used because it does not provide additional meaning or accuracy.

### 11.1.1 Measurable disease

Protocol 2011-0465 ASeptember 6, 2017 Page 43 of 50

Measurable lesions are defined as those that can be accurately measured in at least one dimension (longest diameter to be recorded) as  $\geq 20$  mm with conventional techniques (CT, MRI, x-ray) or as  $\geq 10$  mm with spiral CT scan. All tumor measurements must be recorded in millimeters (or decimal fractions of centimeters). For CNS lesions (hemangioblastomas), measurable lesions are defined as measuring at least 5mm in diameter. This change has been made in recognition of the fact that CNS lesions that equal or exceed 10mm (1cm) may already be symptomatic and require surgical intervention. In order to capture patients in a disease state where therapeutic intervention may be of benefit, lesions measuring 5mm are considered measurable.

## 11.1.2 Non-measurable disease

All other lesions (or sites of disease), including small lesions (longest diameter <20 mm with conventional techniques or <10 mm using spiral CT scan), are considered non-measurable disease. Bone lesions, leptomeningeal disease, ascites, pleural/pericardial effusions, lymphangitis cutis/pulmonis, inflammatory breast disease, abdominal masses (not followed by CT or MRI) are all non-measurable.

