## **3.0 PATIENT SELECTION**

- 3.1 Inclusion Criteria
  - 1. Subjects must provide written informed consent prior to performance of study-specific procedures or assessments, and must be willing to comply with treatment and follow-up. Procedures conducted as part of the subject's routine clinical management (e.g., blood count, imaging study) and obtained prior to signing of informed consent may be utilized for screening or baseline purposes provided these procedures are conducted as specified in the protocol.
  - 2. Eastern Cooperative Oncology Group (ECOG) performance status of  $\leq 2$ .
  - 3. Genetically confirmed diagnosis of VHL or measurable disease consistent with the clinical diagnosis of VHL. (Please refer to criterion #5)

Protocol 2011-0465 ASeptember 6, 2017 Page 14 of 50

- 4. Measurable disease criteria:
  - At least one measurable VHL related lesion, which is undergoing surveillance, and patient is not at immediate risk of needing intervention for this or other lesions. Biopsy is not required given the known likely etiology and natural history in the setting of a positive genetic test.
    - a. Brain: asymptomatic hemangioblastoma,  $\geq 0.5$  cm
    - b. Spine: asymptomatic hemangioblastoma,  $\geq 0.5$  cm
    - c. Renal: solid mass suspicious for RCC ≥1 cm or cystic mass (Bosniak 3-4) ≥1 cm.
    - d. Pancreas: solid mass  $\geq 1$  cm and  $\leq 3$  cm suspicious for neuroendocrine tumor, or neuroendocrine tumor > 3 cm but not considered operable.
    - e. Eye: asymptomatic peripapillary and/or macular hemangioblastoma, any size
    - f. Adrenal: asymptomatic or controlled pheochromocytoma greater than 1cm in size
- 5. Patients may have received prior VHL-related systemic therapy, provided not within 14 days or five half-lives of a drug (whichever is longer) prior to the first dose of pazopanib.

Protocol 2011-0465 ASeptember 6, 2017 Page 15 of 50

6. Adequate organ-system function as defined in Table 4.

System	Laboratory Values
Hematologic	
Absolute neutrophil count	$\geq 1.5 \text{ X } 10^{9}/\text{L}$
(ANC)	
Hemoglobin a	$\geq 9 \text{ g/dL} (5.6 \text{ mmol/L})$
Platelets	≥100 X 10  /L
Prothrombin time (PT) or	≤1.2 X ULN
international normalized ratio (INR) b	
Activated partial thromboplastin	≤1.2 X ULN
time (aPTT)	
Hepatic	
Total bilirubin	≤1.5 X ULN
Alanine amino transferase	≤2.0 X ULN
(ALT) and Aspartate	
aminotransferase (AST) c	
Renal	

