## 7.0 CLINICAL AND LABORATORY EVALUATIONS

- 7.1 Pre-treatment Evaluations
- 7.1.1 Within 8 weeks of signing informed consent:
- All the participants must have signed a consent form agreeing to participate in the study.
- Radiographic examination shall include CNS MRI (brain, cervical and thoracic spine, and saggital T1 post contrast view of the lumbar spine performed in same study and at same time as MRI of cervical and thoracic spine MRI) and CT scans of the chest and abdomen if evaluable lesions exist in these regions. MRI of the abdomen is allowed instead of CT. Appropriate additional studies should be obtained to fully define the extent and severity of existing or suspected VHL disease. Retinal examination will be performed for those patients with known or suspected retinal involvement.
- An electrocardiogram (ECG) will be completed to evaluate heart health.
- Those with a known pheochromocytoma should have serum or urinary evaluation for metanephrines and be under the care of an endocrinologist for management for changes in blood pressure at initiation of therapy

Protocol 2011-0465 ASeptember 6, 2017 Page 34 of 50

- 7.1.2 Within two weeks of study entry:
  - All patients must undergo a complete history and physical examination including vital signs, ECOG performance status, height, and current weight. Concurrent non-VHL disease and medical therapy must be documented. On-study forms must be filled out completely. All prior anti-VHL treatment must be recorded in proper detail. Laboratory studies shall include CBC w/differential, platelet count, chemistry panel (albumin, alkaline phosphatase, BUN, calcium, creatinine, glucose, LDH, phosphorus, Liver Function Test (total bilirubin, SGOT[AST] and/or SGPT[ALT]), sodium, potassium, carbon dioxide, chloride, lipase, PT, PTT. Urine protein creatinine ratio. Serum pregnancy test in female patients of childbearing potential (not postmenopausal for at least one year or not surgically capable of bearing children) will also be included.
  - Optional baseline blood will be collected for correlative studies (approximately 30cc).
  - Any residual toxicity from prior therapies should be recorded by using the grading schema in NCI Common Toxicity Criteria v4.0.
  - 7.2 Evaluation During Treatment

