- MRI Scans: dynamic contrast-enhanced and diffusion-weighted magnetic resonance imaging of brain and spinal column. Up to 5 of the largest CNS lesions will be measured in the single longest dimension per RECIST guidelines. MRI of the abdomen will follow same rules as for CNS lesions.
- Retinal examination: fluorescein angiography with photographs, color testing, visual field testing and echography as needed. Please refer to Appendix C, Recommendations for Retinal examination and Follow-up, for complete details on

Protocol 2011-0465 ASeptember 6, 2017 Page 45 of 50

ophthalmologic evaluation.

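### The minimum target-lesion size for renal and pancreatic lesions on MRI is inconsistent: 10 mm at entry, but 20 mm or 5 mm for response, depending on how Section 11.2 is read

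*Combined protocol and SAP*

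**What the plan says.** Four parts of the protocol bear on whether an abdominal lesion seen on MRI can be a target lesion.

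- **Entry (3.1, item 4).** The patient needs "At least one measurable VHL related lesion, which is undergoing surveillance". The renal entry reads "Renal: solid mass suspicious for RCC ≥1 cm or cystic mass (Bosniak 3-4) ≥1 cm". Pancreatic solid masses qualify from 1 cm. No imaging method is attached to either size.
- **Imaging method (7.1.1).** "MRI of the abdomen is allowed instead of CT".
- **Measurability (11.1.1 and 11.1.2).** The 20 mm minimum applies to lesions measured "with conventional techniques (CT, MRI, x-ray"), and 10 mm is reserved for spiral CT. CNS hemangioblastomas have their own minimum of 5 mm. Anything smaller falls under 11.1.2: "small lesions (longest diameter <20 mm with conventional techniques or <10 mm using spiral CT scan), are considered non-measurable disease".
- **Measurement guidelines (11.2).** Only helical CT is used, with up to 5 renal and 3 pancreatic lesions measured. On MRI, up to 5 CNS lesions are measured in the single longest dimension. The next sentence is "MRI of the abdomen will follow same rules as for CNS lesions".

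The primary efficacy measure in 12.1 is the RECIST CR+PR rate at 24 weeks in up to 40 patients. Section 11.1.5 has kidney, pancreas, CNS and retina summed separately.

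**The concern.** One lesion can be measurable when the patient is enrolled and non-measurable when response is scored, with nothing changed but the scanner. Only target lesions enter the baseline sum (11.1.3), and PR is defined as a 30% fall in that sum (11.3.1). Lesions classed as non-target need not be measured at all (11.1.4), so their sizes may never be recorded. That would also cost data for the secondary objective on growth of target lesions.

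If the text is left as it stands, whoever reads the scans must choose among 5, 10 and 20 mm, and that choice decides which lesions, and possibly which patients, can contribute a response.

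**Working it through.** **1. The minimum for a renal or pancreatic lesion, by source**

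| Source | Helical CT | MRI |
|---|---|---|
| Entry, 3.1 | 10 mm | 10 mm |
| Response, 11.1.1/11.1.2 alone | 10 mm | 20 mm |
| Response, if the 11.2 sentence covers size | 10 mm | 5 mm |

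Entry and response agree on helical CT and disagree on MRI under either reading.

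**2. The 20 mm reading.** An abdominal MRI lesion of 10 to under 20 mm is non-target. An organ with only such lesions has no sum and no possible size-based PR. If they are the patient's only lesions, the patient has no baseline sum. In the overall-response table of 11.3.3, every row leading to CR, PR or SD needs a rating of target lesions. Section 12.1 defines failures and inevaluable patients but does not mention a patient without a target lesion.

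**3. The 5 mm reading.** An abdominal lesion of 5 to under 10 mm can be a target on MRI but not on CT. In an organ whose only target is 5 mm, 1 mm of growth meets the 20% progression criterion (1/5 = 20%); on CT that lesion would not be a target.

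**4. Lesion caps.** If the 11.2 sentence carries over the CNS number rule, the pancreatic cap becomes 5 on MRI against 3 on CT.

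**5. How common 1-2 cm lesions might be.** Inputs from Section 2.3.1: baseline mean (SE) of 2.41 (0.21) cm for renal cell carcinoma and 1.89 (0.28) cm for pancreatic neuroendocrine tumors (NET), from the sunitinib Table 2. That table gives no n, so lesion counts of 18 and 5 are borrowed from the sunitinib Table 1. Sizes are assumed normal, and SD = SE × √n.

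- Renal: SD = 0.21 × √18 = 0.891. P(<2) = Φ(−0.460) = 0.323; P(<1) = Φ(−1.583) = 0.057. P(1-2 cm) = 0.266, about 27%.
- NET: SD = 0.28 × √5 = 0.626. P(<2) = Φ(0.176) = 0.570; P(<1) = Φ(−1.422) = 0.078. P(1-2 cm) = 0.492, about 49%.

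The borrowed n is uncertain, so I also tried smaller values. With n = 9 for renal (SD 0.630) the share is 0.258 − 0.013 = 0.245. With n = 3 for NET (SD 0.485) it is 0.590 − 0.033 = 0.556 before rounding of the terms. The shares move to about 25% and 56%.

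**6. Effect on the endpoint.** The plan's figure first: at n = 40 the largest SE is √(0.25/40) = 0.079, which agrees with the stated limit of 0.08. The normal half-width is 1.96 × 0.079 = 15.5%, against the stated 15%. Now let k of the 40 patients have no target lesion; k is an assumption.

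| k | Excluded: worst-case SE = √(0.25/(40−k)) | Excluded: half-width | Kept as non-responders: 30% × (40−k)/40 |
|---|---|---|---|
| 0 | 0.079 | 15.5% | 30% |
| 4 | 0.083 | 16.3% | 27% |
| 8 | 0.088 | 17.3% | 24% |
| 12 | 0.094 | 18.5% | 21% |
| 16 | 0.102 | 20.0% | 18% |

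The last column takes a 30% response rate among scorable patients as an illustration. Under the 5 mm reading k = 0. The stopping boundaries in 12.1 were calculated without reference to lesion size and do not change.

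**The case against.** The best defence is that 11.2 already settles the matter: abdominal MRI follows the CNS rules, the CNS minimum is 5 mm, so every eligible lesion is measurable. Section 11.1.2 seems to lean the same way, since it lists abdominal masses as non-measurable only when they are not followed by CT or MRI. This is a possible reading, but not a secure one. The sentence directly follows a rule on the number and dimension of lesions, and 11.1.5 points to 11.2 for the number of lesions per site. The reason given for 5 mm, that CNS lesions of 1 cm may already be symptomatic, is specific to the CNS. The remark on abdominal masses does not lift the size limit in the sentence before it.

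Two further points stand. Section 11.2 requires the same technique for each lesion throughout, so percentage change is always within one modality; what differs is which lesions are selected. And a target minimum below the entry minimum is not in itself a contradiction.

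A reader might infer that patients with 1-2 cm abdominal lesions on MRI cannot be scored on the primary endpoint. The documents do not support that. Even at 20 mm, a patient lacks a target only if no other lesion qualifies. A CNS lesion of at least 5 mm, an abdominal lesion of at least 20 mm, or an abdominal lesion of at least 10 mm followed by helical CT supplies one. Non-target disease can still be rated under 11.3.2; what is lost is a size-based PR.

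A reader might also take the shares below 2 cm (32% renal, 57% NET) as the extent of the problem. Those include lesions under 1 cm, which lie outside the conflict, and they count lesions rather than patients.

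**Conclusion.** The inconsistency is real and lies in the text itself. For abdominal MRI, the response section gives a minimum of either 20 mm or 5 mm, and neither equals the 10 mm used at entry and on helical CT. Followed literally, the 20 mm rule removes eligible lesions from the sum on which PR, and so the CR+PR rate, depends. It should be corrected.

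The size of the effect cannot be fixed from the documents, which give neither the frequency of abdominal MRI nor the number of patients with no other target lesion. The estimates of about 27% of renal and 49% of NET lesions at 1-2 cm rest on normal sizes, on lesion counts taken from a different table, and for NET on five lesions. Section 2.3.1 describes the size changes by organ site per individual, so the borrowed counts may not be the right n. These shares show that the size band is not rare; they are not an estimate of patients lost. If 4 to 8 of 40 patients were affected and kept as non-responders, a 30% rate among scorable patients would appear as 27% to 24%.

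**What to change.** Amend the wording as follows.

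1. In 11.1.1 and 11.1.2, state one minimum for renal and pancreatic target lesions on either helical CT or MRI, aligned with the 10 mm entry limit, and take abdominal MRI out of the 20 mm list.
2. In 11.2, replace the abdominal MRI sentence with the caps already used for CT: up to 5 renal and 3 pancreatic lesions, in the single longest dimension. Limiting that sentence to number and dimension would not be enough, because the pancreatic cap would still be 5 on MRI and 3 on CT.
3. In 11.3.3 or 12.1, state how a patient without a target lesion enters the CR+PR denominator.

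The cost is a text amendment to these sections. Sample size, stopping boundaries and visit schedule are unchanged. If patients have already been assessed, confirm which minimum was applied to their abdominal MRI lesions and, where it differed, reassess from the stored images.

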### 11.1.3 Target lesions

All measurable lesions up to a maximum of five lesions per organ and 10 lesions in total, representative of all involved organs, should be identified as target lesions and recorded and measured at baseline. Target lesions should be selected on the basis of their size (lesions with the longest diameter) and their suitability for accurate repeated measurements (either by imaging techniques or clinically). A sum of the longest diameter (LD) for all target lesions will be calculated and reported as the baseline sum LD. The baseline sum LD (per target organ as per Section 11.1.5) will be used as reference by which to characterize the objective tumor response.

### 11.1.4 Non-target lesions

All other lesions (or sites of disease) should be identified as non-target lesions and should also be recorded at baseline. Non-target lesions include measurable lesions that exceed the maximum numbers per organ or total of all involved organs as well as non-measurable lesions. Measurements of these lesions are not required, but the presence or absence of each should be noted throughout follow-up.

### 11.1.5 Rationale for Modification to RECIST Criteria

Patients with VHL have a germline genetic mutation, which displays differential organ phenotypes. Due to the same mechanisms, it is reasonable to assume that responses to targeted therapy may be different in various organ-sites as a result of epigenetic, environmental, and circulatory differences. Using strict RECIST criteria (such as using the sum of all lesions) will lead to potentially significant loss of

Protocol 2011-0465 ASeptember 6, 2017 Page 44 of 50

important information. For the purposes of this study, imaging-based measurements will follow RECIST criteria except for the following conditions:

- Target organ systems will be uncoupled and evaluated separately. Summation of lesion size will be performed separately for the kidney, pancreas, CNS (brain+spine), and retina, and changes from baseline compared using these measurements.
- The number of lesions measured from each site will be modified (specified in Section 11.2, Guidelines for Evaluation of Measurable Disease), as there may be innumerable lesions present, some probably too small to give reproducible and accurate measurements.
- 11.2 Guidelines for Evaluation of Measurable Disease

All measurements should be taken and recorded in metric notation using a ruler or calipers. All baseline evaluations should be performed as closely as possible to the beginning of treatment and not more than 6 weeks before the beginning of the treatment.

The same method of assessment and the same technique should be used to characterize each identified and reported lesion at baseline and during follow-up. Imaging-based evaluation is preferred to evaluation by clinical examination when both methods have been used to assess the antitumor effect of a treatment.

- CT scans: spiral, multiphasic, contrast-enhanced computed tomography of abdomen and pelvis with thin-cuts (5 mm) of adrenals, kidneys, and pancreas. Multi-channel helical CT scan only will be used, as this will provide the most reproducible and reliable size measurements, particularly for lesions in the range of 1 cm.
- CT Interpretation: all CT studies will be evaluated by a radiologist according to standard practice. Up to 5 of the largest renal lesions and 3 of the largest pancreatic lesions will be measured in the single longest dimension per RECIST guidelines.
- MRI Scans: dynamic contrast-enhanced and diffusion-weighted magnetic resonance imaging of brain and spinal column. Up to 5 of the largest CNS lesions will be measured in the single longest dimension per RECIST guidelines. MRI of the abdomen will follow same rules as for CNS lesions.
- Retinal examination: fluorescein angiography with photographs, color testing, visual field testing and echography as needed. Please refer to Appendix C, Recommendations for Retinal examination and Follow-up, for complete details on

Protocol 2011-0465 ASeptember 6, 2017 Page 45 of 50

ophthalmologic evaluation.

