11.3 Response Criteria

11.3.1 Evaluation of target lesions (this will be an organ-specific evaluation, please see Section 11.1.5 *Rationale For Modified RECIST Criteria*)

Complete Response (CR):	Disappearance of all target lesions		
Partial Response (PR):	At least a 30% decrease in the sum of the longest diameter (LD) of target lesions, taking as reference the baseline sum LD		
Progressive Disease (PD):	At least a 20% increase in the sum of the LD of target lesions, taking as reference the smallest sum LD recorded since the treatment started or the appearance of one or more new lesions		
Stable Disease (SD):	Neither sufficient shrinkage to qualify for PR nor sufficient increase to qualify for PD, taking as reference the smallest sum LD since the treatment started		

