11.3.3 Evaluation of best overall response

The best overall response is the best response recorded from the start of the treatment until disease progression/recurrence (taking as reference for progressive disease the smallest measurements recorded since the treatment started). The patient's best response assignment will depend on the

Protocol 2011-0465 ASeptember 6, 2017 Page 46 of 50

Target Organ Lesions	Non-Target Organ Lesions	New Lesions	Overall Response
CR	CR	No	CR
CR	Incomplete response/SD	No	PR
PR	Non-PD	No	PR
SD	Non-PD	No	SD
PD	Any	Yes or No	PD
Any	PD	Yes or No	PD
Any	Any	Yes	PD

achievement of both measurement and confirmation criteria.

Note:

- X For the purposes of this study, response rate (RR) is based on CR+PR+SD.
- X Patients with a global deterioration of health status requiring discontinuation of treatment without objective evidence of disease progression at that time should be classified as having "symptomatic deterioration." Every effort should be made to document the objective progression, even after discontinuation of treatment.
- X In some circumstances, it may be difficult to distinguish residual disease from normal tissue. When the evaluation of complete response depends on this determination, it is recommended that the residual lesion be investigated (fine needle aspirate/biopsy) before confirming the complete response status.

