12.1 Design and sample size/power

In this study, we will treat up to 40 patients with VHL who have measurable VHL related lesions. Patients will receive Pazopanib 800mg PO daily for up to 24 weeks. Patients may choose to continue the regimen beyond 24 weeks until evidence of objective disease progression. Efficacy will be determined by the RECIST overall response rate (CR+PR) at 24 weeks. Early termination due to progressive disease or toxicity will be considered as a failure. Patients not completing 1 month of therapy due to a reason other than drug toxicity or progressive disease will be considered inevaluable. We will monitor for any lesion progression (PD) and drug discontinuation due to toxicity (DD) during the whole period of the treatment simutaneously. If there is a high probability that the PD rate exceeds 20% or the DD rate exceeds 10%, the trial will be stopped early and the drug will not be considered of interest for further study. Formally, the study will be terminated if Pr(PD Rate > 0.20 | Data) > 0.90 or Pr(DD)Rate > 0.10 | Data) > 0.90. The assumed prior distributions for PD rate and DD rate are Beta (0.2, 0.8) and Beta (0.1, 0.9), respectively, with one patient's worth of information. The study will be monitored in cohorts of 10 patients. Consideration to stop the trial will be given according to the stopping boundaries in Table 1. The operating characteristics for these stopping rules are summarized in Table 2, based on 10,000 simulations. Specifically, if the PD rate is 20% and DD rate is 0.10, then there is a 27% chance to stop the trial early and the average expected number of patients

Protocol 2011-0465 ASeptember 6, 2017 Page 48 of 50

treated will be 33. On the other hand, if (PD rate, DD rate) are (0.10, 0.05), or (0.10, 0.30), then the early stopping probabilities will be 3% and 94% and the average numbers of patients treated are expected at 39 and 16, respectively. If the trial continues to the end with 40 patients treated, we will be able to estimate the response rate at 24 weeks with standard error not larger than 0.08, i.e., the half length of the 95% confidence interval will not exceed 15%.

Total Number of Patients Treated	Stop if number of Progressions >=	Stop if number of Drug Discontinuation (due to Toxicity) >=
10	4	3
20	7	5
30	10	6

Table 1. Stopping boundaries for PD and DD monitoring.

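### Response rate is CR+PR+SD in section 11.3.3 but CR+PR in section 12.1, and the rule for combining organs with different results into one patient-level response is unclear

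*Combined protocol and SAP*

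**What the plan says.** Section 11 scores response organ by organ. Section 11.1.3: "The baseline sum LD (per target organ as per Section 11.1.5) will be used as reference by which to characterize the objective tumor response". Section 11.1.5: "Target organ systems will be uncoupled and evaluated separately. Summation of lesion size will be performed separately for the kidney, pancreas, CNS (brain+spine), and retina", because "it is reasonable to assume that responses to targeted therapy may be different in various organ-sites". Section 11.3.1 adds that "this will be an organ-specific evaluation".

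The table in section 11.3.3 then turns one target entry, one non-target entry and the presence of new lesions into an overall response. A note under it says: "For the purposes of this study, response rate (RR) is based on CR+PR+SD".

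Section 12.1 sets the efficacy measure: "Efficacy will be determined by the RECIST overall response rate (CR+PR) at 24 weeks", and adds: "Early termination due to progressive disease or toxicity will be considered as a failure". It promises that 40 patients give a standard error of at most 0.08 and a 95% interval half-length of at most 15%. Section 12.2 plans to estimate the response rate with a 95% posterior credible interval. It does not say which response categories count, and it gives no prior for this rate.

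**The concern.** The two definitions differ on whether SD counts as success. Section 2.5 itself warns that some VHL lesions grow slowly, so many patients may be stable at 24 weeks. With no control arm, a rate that includes SD means something quite different from one that does not. Both sentences are current text, and an analyst could follow either.

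The second difficulty is that a patient with kidney and CNS target lesions has two target results, while section 12.1 needs one. Section 11.1.5 gives differing organ response as the reason for uncoupling, so PR in one organ with SD in another is an expected pattern. The two issues interact. A patient with kidney PR and CNS SD is a responder under CR+PR+SD whatever the organ rule, but under CR+PR the organ rule alone decides. If neither is fixed in advance, the efficacy estimate could depend on a choice made after the data are seen.

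**Working it through.** **The plan's own figures.**
- Worst-case standard error at n = 40: sqrt(0.25/40) = 0.079, so the stated bound of 0.08 holds.
- Wald half-width: 1.96 x 0.0791 = 15.5%, slightly above the stated 15%. It reaches 15% or more only for 15 to 25 responders of 40 (37.5% to 62.5%).
- 95% credible half-width at 20/40: 14.9% with a flat Beta(1,1) prior and 15.04% with Beta(0.5,0.5).
- Stopping boundaries from the stated priors and the 0.90 cut-off: 4/7/10 for PD and 3/5/6 for DD, exactly as printed.
- Operating characteristics, computed exactly over looks at 10, 20 and 30 patients with PD and DD independent: all nine rows agree within 0.01 for early stopping and about 0.2 patients for expected number. For example, at PD 0.20 and DD 0.10 the result is 0.273 and 33.1, against the printed 0.27 and 33.1.

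**Distance between the two definitions.** Inputs are the lesion counts in the sunitinib best-response table, section 2.3.1.

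| Lesion type | CR+PR | CR+PR+SD |
|---|---|---|
| Hemangioblastoma | 0/21 = 0% | 19/21 = 90% |
| Renal cell carcinoma | 6/18 = 33% | (6+10)/18 = 89% |

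Counts are used because the percentages printed in the renal row do not match them: 10 is shown as 67% and 2 as 10%, whereas 10/18 = 56% and 2/18 = 11%. The counts do add up (6+10+2 = 18). They concern another drug and single lesions, so they show scale and do not predict the result.

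**Combining organs.** The rows of the 11.3.3 table set against section 11.3.2:
- The table has one target column. No row has two target entries.
- The row for PR with a non-target result short of PD gives PR. Section 11.3.2 defines the non-target SD entry as persistence of non-target lesions, so applying this row to a second target organ is an analogy.
- Section 12.1 says "We will monitor for any lesion progression (PD) and drug discontinuation due to toxicity (DD"), but this describes the monitored endpoint. Section 11.3.1 defines PD on the organ sum, so it does not supply a cross-organ response rule.
- CR or PR in one organ with PD in another falls under the table's PD row. Yet the failure sentence in 12.1 is worded for early termination, and section 7.4 can keep a patient who progresses and needs surgery on study when other organs benefit.

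One patient with CR/PR in one organ and SD in another is worth 1/40 = 2.5 points, between counting a response in any organ and requiring it in every organ.

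**Timing and confirmation.** Section 12.1 fixes 24 weeks, whereas 11.3.3 takes the best response until progression. Scans fall at weeks 12 and 24, and 11.4.1 requires confirmation at least 6 weeks after the criteria are first met. A response first seen at week 24 cannot be confirmed before week 24 + 6 = 30.

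**Adrenal.** Section 3.1 item 4f lets a pheochromocytoma over 1 cm qualify a patient, and 11.1.3 asks for targets from all involved organs. Section 11.1.5 names sums for four organ systems, and adrenal is not one of them.

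**The case against.** The best defence concerns the organ rule. The table headings in 11.3.3 refer to target-organ and non-target-organ lesions, which can be read as the organ being scored against disease elsewhere. PR with no PD elsewhere would then be PR. That makes a likely default, so a reader who infers that the protocol has no rule at all goes too far. But sections 11.1.4 and 11.3.2 define the second column by non-target lesions, so the default is not secure.

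The sum over all target lesions, which 11.1.3 also says is calculated, does not fill the gap. The same section makes the per-organ sum the reference, and 11.1.5 rejects the all-lesion sum. It would also change results. With the mean baseline sizes in section 2.3.1 (2.41 cm renal, 0.81 cm hemangioblastoma), a 30% kidney decrease with no CNS change is -0.30 x 2.41/(2.41+0.81) = -22%: PR by organ, SD if pooled.

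It is also fair that response has no null value, threshold or go/no-go rule, and that organ-level analyses are already foreseen (sections 2.6 and 9.1). The harm is confined to one estimate, though it is the efficacy estimate. For adrenal lesions, the five-per-organ cap in 11.1.3 can serve as the count, so only the sum is missing.

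None of this answers the conflict between CR+PR+SD and CR+PR.

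**Conclusion.** The plan is wrong as written on the definition of response rate: sections 11.3.3 and 12.1 contradict each other, and 12.2 does not resolve it. On the sunitinib counts the gap is 90 percentage points for hemangioblastoma and 56 for renal cell carcinoma (16/18 - 6/18 = 10/18), as an indication of scale only.

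The organ-combination rule is unclear, with a likely default by analogy. It is worth 2.5 points per affected patient, assuming 40 evaluable patients. A reader might infer a particular total shift in the primary result; the documents do not support one, because they do not give the number of patients with mixed organ results.

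A reader might also infer that the design fails. It does not: the PD and DD boundaries and operating characteristics reproduce, and the 40-patient sample size does not depend on this point. The adrenal omission and the half-point excess in the stated half-width are minor.

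**What to change.** 1. Keep CR+PR as the response rate in both 11.3.3 and 12.1. Give CR+PR+SD another name in 11.3.3, for example disease control rate, and report it as secondary. Use the same term in 12.2.
2. Before analysis, state one patient-level rule in 11.3.3 and 12.1. For example: responder at 24 weeks = CR or PR in at least one target organ, with no PD in any target organ, no non-target PD and no new lesion up to 24 weeks. State whether the response must still be present at 24 weeks and how the 11.4.1 confirmation applies. A rule without these elements would leave the endpoint open.
3. Report organ-specific CR+PR rates alongside, because this example is the more favourable reading.
4. Minor: add an adrenal sum to 11.1.5, with the 11.1.3 cap as the lesion count. In 12.1, restate the worst-case half-width as 15.5%, or cite the credible interval planned in 12.2 with its prior (flat prior: 14.9%).

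The cost is a few sentences and a few extra tables from data already collected, with no added patients. No scans are added beyond those that 11.4.1 already requires. The organ-specific intervals will be wide, and the stated precision becomes slightly less favourable.
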